 - INR < 1.3 x ULN (or < 3 on anticoagulants);
 - ALT and AST ≤ 2.5 x ULN (≤ 5 x ULN in patients with liver metastases).
 - ECOG performance status 0 – 2.
 - Fully recovered from any previous surgery, prior chemotherapy or radiation therapy (at least 4 weeks since major surgery or prior myelosuppressive chemotherapy). Prior radiotherapy to a single index lesion is not allowed. With the exception of alopecia, patients must have resolution of all acute toxic effects of any prior surgery, radiotherapy, or chemotherapy to NCI CTC (Version 3.0) grade ≤ 1 .
 - Signed informed consent to participate in the study must be obtained from patients after they have been fully informed of the nature and potential risks by the investigator (or his/her designee) with the aid of written information.

Exclusion criteria

- Anticancer therapy within 3 weeks of enrollment including chemotherapy, hormonal therapy, immunotherapy, or radiotherapy.
- The following tumor types will not be included:

- gastrointestinal stromal tumor (except for patients after treatment with imatinib or sunitinib in 1st and 2nd line);
- chondrosarcoma;
- malignant mesothelioma;
- neuroblastoma.
- Prior therapy with RAD001 (everolimus) or other rapamycins (sirolimus, temsirolimus).
- neurotoxicity \geq grade 2 CTC.
- Radiation of the lung.
- Patients taking drugs known to inhibit or induce isoenzyme CYP3A (Table 6-4) are excluded unless the drugs are medically necessary and no substitutes are available. If there are no acceptable substitutes, special precautions should be taken in these patients (section 6.3.5).
- Patients with any concurrent major medical condition liable to compromise the patient's participation in the study (e.g. known HIV infection, uncontrolled diabetes, serious cardiac dysrhythmia or condition, New York Heart Association classification of III or IV, congestive cardiac failure, myocardial infarction within 6 months, unstable angina, chronic or acute renal or liver disease, uncontrolled serious infections including abscess or fistulae, etc.).
- Patients with a history of another malignancy prior to study entry, except curatively treated non-melanotic skin cancer or carcinoma in-situ cervical cancer unless in complete remission or no evidence of disease and off all therapy for that disease for a minimum of 5 years.

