2. For more severe toxicity (grade 2 in which case patients have pain but are able to maintain adequate oral alimentation, or grade 3 in which case patients cannot maintain adequate oral alimentation), the suggested treatments are **topical analgesic mouth treatments (i.e. local anesthetics, such as benzocaine, butyl aminobenzoate, tetracaine hydrochloride,**

- menthol, or phenol)** with or without **topical corticosteroids**, such as triamcinolone oral paste 0.1% (Kenalog in Orabase[®]).
3. Agents containing hydrogen peroxide, iodine, and thyme derivatives may tend to worsen mouth ulcers. It is preferable to avoid these agents.
 4. Antifungal agents must be avoided unless a fungal infection is diagnosed. In particular, systemic imidazole antifungal agents (ketoconazole, fluconazole, itraconazole, etc.) should be avoided in all patients due to their strong inhibition of RAD001 metabolism, thus leading to higher RAD001 exposures. Therefore, topical antifungal agents are preferred if an infection is diagnosed. Similarly, antiviral agents such as acyclovir should be avoided unless a viral infection is diagnosed.

Note: Stomatitis/oral mucositis should be appropriately graded using the functional grading given on the NCI-CTC for Adverse Events, version 3.0.

Management of hyperlipidemia and hyperglycemia

Treatment of hyperlipidemia should take into account the pre-treatment status and dietary habits. Blood tests to monitor hyperlipidemia must be taken in the fasting state. Grade 2 or higher hypercholesterolemia (> 300mg/dL or 7.75mmol/L) or grade 2 or higher hypertriglyceridemia (> 2.5 x ULN) should be treated with a statin or appropriate lipid-lowering medication, in addition to diet. Patients should be monitored clinically and through serum biochemistry for the development of rhabdomyolysis and other adverse events as required in the product label/data sheets for HMG-CoA reductase inhibitors.

Note: Concomitant therapy with fibrates and an HMG-CoA reductase inhibitor is associated with an increased risk of a rare but serious skeletal muscle toxicity manifested by rhabdomyolysis, markedly elevated creatine kinase (CPK) levels and myoglobinuria, acute renal failure and sometimes death. The risk versus benefit of using this therapy should be determined for individual patients based on their risk of cardiovascular complications of hyperlipidemia.

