The investigator should promote compliance by instructing the patient to take the study drug exactly as prescribed and by stating that compliance is necessary for the patient's safety and the validity of the study. The patient should be instructed to contact the investigator if he/she is unable for any reason to take the study drug as prescribed.

All dosages prescribed and dispensed to the patient and all dose changes during the study must be recorded on the Dosage Administration Record CRF.

Management of Hepatitis reactivation

Monitoring and prophylactic treatment for hepatitis B reactivation

Table 4 provides details of monitoring and prophylactic therapy according to the baseline results of viral load and serologic markers testing.

Table 6-4 Action to be taken for positive baseline hepatitis B results

Test	Result	Result	Result	Result	Result
HBV-DNA	+	+ or -	-	-	-
HBsAg	+ or -	+	-	-	-
HBs Ab	+ or -	+ or -	+ and no prior HBV vaccination	+ or -	- or + with prior HBV vaccination
HBc Ab	+ or -	+ or -	+ or -	+	-

Test	Result	Result	Result	Result	Result
Recommendation	Prophylaxis treatment should be started 1-2 weeks prior to first dose of study drug Monitor HBV-DNA approximately every 4-8 weeks		No prophylaxis Monitor HBV-DNA approximately every 4 weeks		No specific action

Antiviral prophylaxis therapy should continue for at least 4 weeks after last dose of study drug.

For patients who have already been randomized and received study drug prior to the approval of the amendment, the same process should be followed at the patient's next visit. The first HBV-DNA result would be regarded as baseline.

For hepatitis B reactivation, definition and management guidelines, see Table 5 Guidelines for management of hepatitis B.

Table 6-5 Guidelines for management of hepatitis B

HBV reactivation (with or without clinical signs and symptoms)*	

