6.3.5 Other concomitant medications

Inhibitors of CYP3A4 and/or PgP

Co-administration with strong inhibitors of CYP3A4 (e.g., ketoconazole, itraconazole, ritonavir) or P-glycoprotein (PgP) should be avoided.

Co-administration with moderate CYP3A4 inhibitors (e.g., erythromycin, fluconazole) or PgP inhibitors should be used with caution. If patient requires co-administration of moderate CYP3A4 inhibitors or PgP inhibitors, reduce the dose of everolimus to half the currently used dose. Additional dose reductions to every other day may be required to manage toxicities. If

the inhibitor is discontinued the everolimus dose should be returned to the dose used prior to initiation of the moderate CYP3A4/PgP inhibitor.

Seville orange, star fruit, grapefruit and their juices affect P450 and PgP activity. Concomitant use should be avoided.

Inducers of CYP3A4 and/or PgP

Avoid the use of strong CYP3A4 inducers. If patient requires co-administration of strong CYP3A4 inducers (i.e., phenytoin, carbamazepine, rifampin, rifabutin, phenobarbital, St. John's wort), an increase in the dose of everolimus up to twice the currently used daily dose should be considered, using 5 mg increments every other day – 5 mg increments daily. Enzyme induction usually occurs within 7-10 days, therefore everolimus dose should be increased by one increment 7 days after the start of the inducer therapy. If no safety concerns are seen within the next 7 days, the dose can be increased again one additional increment up to a maximum of twice the daily dose used prior to initiation of the strong CYP3A4 inducer.

This dose adjustment of everolimus is intended to achieve similar AUC to the range observed without inducers. However, there are no clinical data with this dose adjustment in patients receiving strong CYP3A4 inducers. If the strong inducer is discontinued the everolimus dose should be returned to the dose used prior to initiation of the strong CYP3A/PgP inducer.

Table 6-7 Clinically relevant drug interactions: substrates, inducers, and inhibitors of isoenzyme CYP3A

INDUCERS
Barbiturates, carbamazepine, glucocorticoids, modafinil, oxcarbazepine, phenobarbital, phenytoin, pioglitazone, rifabutin, rifampin, St. John's wort, troglitazone, efavirenz, nevirapine, topiramate
INHIBITORS

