Strong inhibitors: clarithromycin, conivaptan, indinavir, itraconazole, ketoconazole, lopinavir, mibefradil, nefazodone, nelfinavir, ritonavir, saquinavir, telithromycin, troleandomycin, voriconazole, Posaconazole (Krishna et al, 2009)
Moderate inhibitors: aprepitant, atazanavir, cimetidine, ciprofloxacin, darunavir, diltiazem, erythromycin, fluconazole, grapefruit juice, imatinib, tofisopam, verapamil,

Table 6-8 Clinically relevant drug interactions mediated by PgP

PgP Substrates	PgP Inhibitors in vivo	PgP Inducers
digoxin, fexofenadine, indinavir, vincristine, colchicine, topotecan, paclitaxel	amiodarone, azithromycin, captopril, carvedilol, clarithromycin, conivaptan, cyclosporine, diltiazem, elacridar, erythromycin, felodipine, (GF120918),	rifampin, St John's wort

PgP Substrates	PgP Inhibitors in vivo	PgP Inducers
	itraconazole, ketocoazole, lopinavir, (LY335979), mibefradil, nifedipine, nitrendipine, (PSC833), quinidine, ranolazine, ritonavir, talinolol, valsopodar, verapamil	

Reference:

Internal Clinical Pharmacology Drug-drug interaction (DDI) memo, updated Dec. 2, 2009, which summarizes DDI data from three sources including the FDA's "Guidance for Industry, Drug Interaction Studies, the University of Washington's Drug Interaction Database, and Indiana University School of Medicine's Drug Interaction Table. "

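### Protocol 6.3.3 and 6.3.5 conflict on fluconazole, 6.3.5 puts PgP inhibitors under two rules that Table 6-8 cannot separate, and the CYP3A exclusion criterion cites the wrong table

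*Protocol*

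**What the plan says.** **Fluconazole.** Protocol section 6.3.3, under the management of stomatitis, oral mucositis and mouth ulcers, states that "systemic imidazole antifungal agents (ketoconazole, fluconazole, itraconazole, etc.) should be avoided in all patients due to their strong inhibition of RAD001 metabolism". It adds that "topical antifungal agents are preferred if an infection is diagnosed". It neither refers to section 6.3.5 nor says what to do with the RAD001 dose if a systemic azole is given.

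Section 6.3.5 puts the same drug in another class: "Co-administration with moderate CYP3A4 inhibitors (e.g., erythromycin, fluconazole) or PgP inhibitors should be used with caution". The next sentence gives the dose rule: "If patient requires co-administration of moderate CYP3A4 inhibitors or PgP inhibitors, reduce the dose of everolimus to half the currently used dose". Table 6-7 agrees with 6.3.5: "Moderate inhibitors: aprepitant, atazanavir, cimetidine, ciprofloxacin, darunavir, diltiazem, erythromycin, fluconazole, grapefruit juice, imatinib".

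**PgP inhibitors.** Section 6.3.5 opens with "Co-administration with strong inhibitors of CYP3A4 (e.g., ketoconazole, itraconazole, ritonavir) or P-glycoprotein (PgP) should be avoided". The caution and half-dose sentences quoted above follow directly and cover PgP inhibitors without saying of what strength. Table 6-8 lists PgP inhibitors in a single column.

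**Exclusion criterion.** Section 5.1 reads "Patients taking drugs known to inhibit or induce isoenzyme CYP3A (Table 6-4) are excluded", with an exception for medically necessary drugs that have no substitute and a further pointer to section 6.3.5. Table 6-4 is titled "Action to be taken for positive baseline hepatitis B results". The CYP3A list is Table 6-7.

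**The concern.** The question is whether a site can find one instruction for a given co-medication. For fluconazole it finds two. One says to avoid the drug in every patient because it inhibits strongly. The other says it is a moderate inhibitor that can be given if needed, with half the RAD001 dose. A site that halves the dose and gives fluconazole follows 6.3.5 and departs from 6.3.3. A site that reads only 6.3.3 and still needs the drug has no dose instruction.

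For PgP inhibitors, one section appears to give both an avoid rule and a half-dose rule, and the drug list does not show which drugs belong to which.

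The situation is foreseeable. Section 1.3.3 reports severe, suspected drug-related, dose-limiting events in 19% of phase I patients, mainly stomatitis, and 6.3.3 itself provides for a diagnosed fungal infection. Section 6.3.3 also says that inhibition raises RAD001 exposure, so the choice of instruction bears on patient safety. The on-treatment rules are still in force: the rationale for Amendment 7 records two patients on drug at 23 July 2013, one in arm II and one in arm III.

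**Working it through.** No figure in the plan depends on this point. The check compares the texts and counts table entries.

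**Step 1: fluconazole, side by side.**

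| | Section 6.3.3 | Section 6.3.5 and Table 6-7 |
|---|---|---|
| Class | strong inhibition, grouped with ketoconazole and itraconazole | moderate, grouped with erythromycin |
| Instruction | avoid, all patients | caution; permitted if required |
| RAD001 dose if given | none stated | half the current dose |

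The rows differ in class, in instruction and in whether a dose rule exists. Section 6.3.5 names ketoconazole and itraconazole under its avoid rule, so for those two the sections agree. Of the three azoles that 6.3.3 names, only fluconazole is classed differently.

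**Step 2: PgP inhibitors.** The first sentence of 6.3.5 can be read in two ways.

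- If the word for strong inhibitors applies to CYP3A4 only, all PgP inhibitors are to be avoided, and the next two sentences contradict this by allowing them with caution at half dose.
- If it applies to PgP as well, strong PgP inhibitors are avoided and the others are halved. That is coherent, but a site then needs to know which PgP inhibitors are strong.

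**Step 3: does Table 6-8 supply the grading?** It does not. The PgP inhibitor column was cross-tabulated against the two CYP3A inhibitor rows of Table 6-7:

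- Entries in Table 6-8, as printed: 26.
- Also strong CYP3A inhibitors in Table 6-7: 7 (clarithromycin, conivaptan, itraconazole, ketoconazole, lopinavir, mibefradil, ritonavir).
- Also moderate CYP3A inhibitors: 3 (diltiazem, erythromycin, verapamil).
- In neither row: 26 − 7 − 3 = 16 (for example amiodarone, captopril, carvedilol, nifedipine).

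The 7 and the 3 can be placed by their CYP3A class. The 16 have no grade of either kind, so under the coherent reading in step 2 no rule can be picked for them. Three of the 16 are bracketed code names. If those are left out, the figures become 26 − 3 = 23 entries and 16 − 3 = 13 that cannot be placed, and the conclusion is the same.

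**Step 4: exclusion criterion.** The table number cited belongs to the hepatitis B actions. Following the criterion's second pointer, to 6.3.5, leads to Table 6-7, so a careful reader recovers the intended list.

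**The case against.** The strongest reply is that the protocol can be read sensibly. Avoiding a drug and preferring a topical agent, followed by caution and a dose rule if the drug is required, looks like a preference with a fallback. The PgP sentences have the coherent reading set out above. The seven drugs found in both the strong CYP3A list and Table 6-8 fall naturally under the stricter rule, and 6.3.5 names three of them there. The wrong table number is recoverable and can no longer affect anyone's entry, because the rationale for Amendment 7 states that enrolment is complete in all three arms.

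Most of this stands. It disposes of the seven overlapping drugs and reduces the table reference to a correction of record. Two things remain. A preference with a fallback does not explain why one section calls fluconazole strong and the other moderate, or why the first extends its instruction to all patients without mentioning the fallback. And the coherent PgP reading needs a grading that Table 6-8 lacks.

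A reader might infer more than the documents support:

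- *That a patient could be given full-dose RAD001 with these drugs.* No text permits it. Section 6.3.3 is silent on dose, which is a gap and not a permission.
- *That grapefruit juice is another contradiction.* Table 6-7 only classifies it. The text of 6.3.5 says to avoid it, and a moderate inhibitor can also be one to avoid.
- *That the exclusion criterion should have covered PgP inhibitors.* Section 6.3.5 allows them at reduced dose, so not excluding those patients is consistent.
- *That the trial's activity estimate is distorted, or that exposure differs twofold.* The half-dose rule compares a patient on an inhibitor with one who is not, so it does not measure an exposure difference between like patients. The documents give no frequency of use.

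**Conclusion.** The point holds in three parts of unequal weight. First, the protocol contradicts itself on fluconazole, in both class and instruction, and the section that says to avoid it gives no dose instruction. Second, section 6.3.5 places PgP inhibitors under two instructions, and 16 of the 26 entries in Table 6-8 (13 of 23 without the bracketed codes) cannot be assigned to either. Third, the exclusion criterion cites the hepatitis B table in place of Table 6-7, which matters only for the record.

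The first two should be corrected because they concern dosing and safety while patients are on treatment. Their practical effect cannot be sized, since nothing in the documents says how often these drugs were given. The counts take Tables 6-7 and 6-8 as printed, allowing for evident misspellings of drug names. Nothing here says which class, rule or dose is right.

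**What to change.** The sponsor must reconcile the fluconazole text so that section 6.3.3, section 6.3.5 and Table 6-7 give the same class and the same instruction, with 6.3.3 referring to 6.3.5 for any dose rule that applies. Section 6.3.5 or Table 6-8 should show which of the two instructions each listed PgP inhibitor falls under. In section 5.1, change the reference from Table 6-4 to Table 6-7. Which instruction applies to each drug is a decision for the sponsor and its clinical pharmacology experts.

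The cost is amendment wording and table edits. No change to the design, sample size or analysis is needed.

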6.3 Treating the patient

6.3.1 Instructions for prescribing and taking the study drug

RAD001 will be dispensed by the study center personnel on an outpatient basis. Patients will be provided with an adequate supply of RAD001 for self-administration at home.

RAD0001 will be dosed starting on Week 1 Day 1. Patients will be instructed to take two tablets of RAD001 orally with a glass of water, once daily at the same time each day, in a fasting state or after no more than a light, fat-free meal. If vomiting occurs, no attempt should be made to replace the vomited dose. Patients should be requested to bring their unused medication, including the empty blister packs, to the clinic at each visit. Compliance should be verified by the investigator's staff through counting the number of tablets consumed between visits.

The investigator (or his/her designee) will document dosage administration and all dose changes during the study in the CRF. The site must maintain an overall drug accountability log for the study, as well as individual accountability records for each patient. The dose, amount dispensed, amount received, and amount remaining unused must be recorded in the source document. Drug accountability will be noted by the field monitor during site visits and at the completion of the study. The patient will be asked to return all unused RAD001 at the end of study treatment.

Patients will be treated with RAD001 until progression of tumor, the occurrence of unacceptable toxicity, or until the investigator or patient decides that continuation is not in the best interest of the patient. Interruption for toxicity should follow the instructions in Table 6.2.

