6.3.3 Management of RAD001 toxicities

Known Undesirable Side Effects of RAD001

Adverse events most frequently observed with RAD001 are rash, stomatitis/oral mucositis, fatigue, headache, anorexia, nausea, vomiting, diarrhea, ocular toxicity and infections. Non-infectious pneumonitis has also been observed. Overall, the most frequently observed laboratory abnormalities include neutropenia, thrombocytopenia, hypercholesterolemia, and/or hypertriglyceridemia. The majority of these AEs have been of mild to moderate severity (CTC grade 1-2).

Table 6-2 Criteria for dose-modification in case of suspected RAD001 toxicity and re-initiation of RAD001 treatment

Toxicity	Actions
Non-hematological toxicity Grade 2 (except pneumonitis, refer to Table 6.3)	If the toxicity is tolerable to the patient, maintain the same dose. If the toxicity is intolerable to patient, interrupt RAD001 until recovery to grade \leq 1. Then reintroduce RAD001 at same dose. If event returns to grade 2, interrupt RAD001 until recovery to grade \leq 1. Then reintroduce RAD001 at the lower dose level.
Grade 3 (except hyperlipidemia)	Interrupt RAD001 until recovery to grade \leq 1. Then reintroduce RAD001 at the lower dose level. For pneumonitis, consider the use of a short course of corticosteroids (see table 6.3).
Grade 3 hyperlipidemia (hypercholesterolemia and/or hypertriglyceridemia)	Should be managed using standard medical therapies.
Grade 4	Discontinue RAD001.
Hematological toxicity Grade 2 Thrombocytopenia (platelets $<$ 75, \geq 50x10 ⁹ /L)	Interrupt RAD001 until recovery to grade \leq 1 (platelets \geq 75x10 ⁹ /L). Then reintroduce RAD001 at initial dose. If thrombocytopenia again returns to grade 2, interrupt RAD001 until recovery to grade \leq 1. Then reintroduce RAD001 at the lower dose level.
Grade 3 Thrombocytopenia (platelets $<$ 50, \geq 25x10 ⁹ /L)	Interrupt RAD001 until recovery to grade \leq 1 (platelets \geq 75x10 ⁹ /L). Then resume RAD001 at one dose level lower. If grade 3 thrombocytopenia recurs, discontinue RAD001.
Grade 4 Thrombocytopenia (platelets $<$ 25x10 ⁹ /L)	Discontinue RAD001.

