Additional chest x-rays or CT scans may be performed when clinically necessary. If non-infectious pneumonitis develops, a consultation with a pulmonologist should be considered. If the patient develops grade 3 pneumonitis, treatment with RAD001 should be interrupted and the patient should be treated as medically indicated (short course corticosteroids, oxygen, etc). Management of non-infectious pneumonitis suspected to be associated with RAD001 and dose modifications instructions are provided in Table 6.3.

Table 6-3 Management of non-infectious pneumonitis

Worst Grade Pneumonitis	Required Investigations	Management of Pneumonitis	RAD001 Dose Adjustment
Grade 1	CT scans with lung windows and required pulmonary function testing includes: spirometry, DLCO, and room air O ₂ saturation at rest. Repeat a chest x-ray/CT scan every 2 cycles until return to baseline.	No specific therapy is required.	Administer 100% of RAD001 dose.
Grade 2	CT scan with lung windows and pulmonary function testing includes: spirometry, DLCO, and room air O ₂ saturation at rest. Repeat each subsequent cycle until return to baseline. Consider a bronchoscopy.	Symptomatic only. Prescribe corticosteroids if cough is troublesome.	Reduce RAD001 dose until recovery to < grade 1. RAD001 may also be interrupted if symptoms are troublesome. Patients will be withdrawn from the study if they fail to recover to < grade 1 within 3 weeks.

Grade 3	CT scan with lung windows and pulmonary function testing includes: spirometry, DLCO, and room air O ₂ saturation at rest. Repeat each subsequent cycle until return to baseline. Bronchoscopy is required	Prescribe corticosteroids if infective origin is ruled out. Taper as medically indicated.	Hold treatment until recovery to < grade 1. May restart protocol treatment within 2 weeks at a reduced dose (by one level) if evidence of clinical benefit.
Grade 4	CT scan with lung windows and required pulmonary function testing includes: spirometry, DLCO, and room air O ₂ saturation at rest. Repeat each subsequent cycle until return to baseline. Bronchoscopy is required.	Prescribe corticosteroids if infective origin is ruled out. Taper as medically indicated.	Discontinue treatment.

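### Table 6-3 times repeat pneumonitis tests by an undefined 'cycle', so none is dated to its 3-week withdrawal rule, and its grade 3 restart threshold differs from Table 6-2

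*Protocol*

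**What the plan says.** Table 6-3 (Protocol 6.3.3) sets the investigations for non-infectious pneumonitis by worst grade. Grade 1: "Repeat a chest x-ray/CT scan every 2 cycles until return to baseline". Grades 2, 3 and 4, for CT and lung function: "Repeat each subsequent cycle until return to baseline".

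The dose column of the same table works in calendar time. Grade 2: reduce the dose (interruption is optional if symptoms are troublesome), and "Patients will be withdrawn from the study if they fail to recover to < grade 1 within 3 weeks". Grade 3: "Hold treatment until recovery to < grade 1", then "May restart protocol treatment within 2 weeks at a reduced dose (by one level) if evidence of clinical benefit".

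Table 6-2, in the same section, has a grade 3 non-haematological row that excepts only hyperlipidaemia. It interrupts drug until recovery to grade 1 or lower and continues: "Then reintroduce RAD001 at the lower dose level. For pneumonitis, consider the use of a short course of corticosteroids (see table 6.3". The row above it is labelled "Grade 2 (except pneumonitis, refer to Table 6.3"; the grade 3 row has no such label.

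Two sentences direct the site. Section 6.3.1 says: "Interruption for toxicity should follow the instructions in Table 6.2". The pneumonitis text of 6.3.3 says that dose-modification instructions for pneumonitis are in Table 6.3.

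**The concern.** There are two separate problems.

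**Unit.** A site cannot look up when a required repeat is due, because nothing in the legible protocol turns a cycle into days. The rule that depends on the result, withdrawal of a grade 2 patient at 3 weeks, is in calendar time. If no image is available by then, a site may withdraw a patient who has recovered or keep one who should leave, and sites may differ. Most grade 2 patients in question would still be taking a reduced dose.

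**Threshold.** A grade 3 patient who improves to symptom-free radiological change may restart at the lower dose under Table 6-2 and must stay on hold under Table 6-3. The two tables give opposite actions for the same patient, for a toxicity that the protocol itself associates with the drug.

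**Working it through.** The plan gives no figure to reproduce. The check is a comparison of the text plus a day count.

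**Step 1: is a cycle defined?** Section 6.2 doses daily. Section 7.4 sets tumour imaging at weeks 8, 16, 28, 40 and 52. The visit schedule in Section 7, as far as it is legible, runs in visits, days and weeks (core weeks 4, 8, 12, 16). Outside Table 6-3 the word appears only in connection with the cell cycle. So no length can be looked up.

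**Step 2: does the grade 2 rule need an image?** Section 6.3.3 describes grade 1 as asymptomatic radiological change. Showing recovery below grade 1 therefore implies an image, if '<' is read literally.

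**Step 3: when does the first required repeat fall?** The cycle length L is not given, so L = 14, 21 and 28 days are assumptions.

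*(a) Cycle counted from diagnosis*, taken as the day of dose reduction or hold. The first repeat is on day L.

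| L (days) | Against grade 2 limit, L − 21 | Against grade 3 window if run from the hold, L − 14 |
|---|---|---|
| 14 | 7 days before | on the day |
| 21 | on the day | 7 days after |
| 28 | 7 days after | 14 days after |

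If the grade 3 window runs from recovery, no day-14 image is implied. The outer bound is then the 21-day interruption limit (6.3.3, 6.3.4; 6.3.6 allows an exception), and the L − 21 column applies.

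*(b) Cycle boundaries fixed by the calendar*, with onset uniform within a cycle. The chance that the next boundary falls within d days is min(1, d/L).

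| L (days) | By day 14 | By day 21 |
|---|---|---|
| 14 | 100% | 100% |
| 21 | 14/21 = 67% | 100% |
| 28 | 14/28 = 50% | 21/28 = 75% |

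Under either reading a 14-day cycle meets the grade 2 limit and a 21-day cycle just meets it. A 28-day cycle misses it under (a) and misses it in 25% of cases under (b).

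**Step 4: does other text supply the date?**
- Additional scans when clinically necessary (6.3.3) and unscheduled scans (7.4) are allowed, but are neither required nor dated.
- Weekly telephone follow-up (6.3.3, 6.3.4) applies to patients who interrupt or stop drug. A dose-reduced grade 2 patient does not trigger it, and a call is not an image.
- Scheduled tumour imaging is 8 weeks apart up to week 16 and then 12 weeks apart (28 − 16 = 40 − 28 = 52 − 40 = 12), so it cannot be relied on within 21 days.

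**Step 5: grade 3 threshold, side by side.**

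| | Table 6-2, grade 3 row | Table 6-3, grade 3 row |
|---|---|---|
| Covers pneumonitis? | Yes, by name | Yes |
| Recovery needed | grade 1 or lower | below grade 1 |
| Patient now at grade 1 | may restart one level lower | stays on hold |

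**The case against.** **A careful site can work this out.** A rule that withdraws at 3 weeks for lack of recovery presupposes that recovery is assessed by then, and the protocol permits extra scans. A monitoring interval that runs until return to baseline also need not coincide with a dosing decision. This is fair. For grade 3 it largely settles the matter: the hold rule already implies an image before a compliant restart, and without one the patient simply stays on hold. For grade 2 it shows that the assessment is implied. It does not supply a required test with a date, and withdrawal is mandatory.

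**Table 6-3 governs.** Section 6.3.3 is the specific instruction, Section 6.3.1 the general one, and the Table 6-2 grade 3 row itself points to Table 6.3. That is the better reading. What stands is that this pointer is attached to the corticosteroid advice, while the explicit exception appears in the grade 2 row only.

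**The '<' may be a lost '≤'.** It appears three times in Table 6-3, and '≤' survives in Tables 6-2 and 6-5, so it may well be literal. That is not settled. If it is a misreading, the threshold point falls, loss of symptoms might be enough to show recovery, and the day counts lose much of their force. The undefined unit remains.

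**Stronger readings that the documents do not support.**
- A reader might infer that the cycle is 28 days and that every limit is missed. Four-weekly core visits, and 2 × 28 days = 8 weeks matching the bimonthly imaging mentioned in 6.3.3, suggest that length but do not state it. Missing every limit also requires the cycle to start at diagnosis.
- A reader might call a restart at grade 1 a dosing error. Table 6-3 itself gives the full dose when the worst grade is 1, so the documents show a conflict between two rules, not that the more permissive one is unsafe.

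**Conclusion.** The point holds as a minor one. Confidence is high that the repeat interval has no defined unit, and that no required repeat is therefore dated to the 3-week grade 2 decision. For assumed cycles of 14 to 28 days the first repeat ranges from before day 21 to 7 days after it. Confidence is moderate for the grade 3 threshold conflict, which rests on '<' being literal.

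A reader might infer that inconsistent withdrawal undermines the week 16 result. The documents give no pneumonitis frequency from which to size that, and no endpoint definition, analysis rule or error rate depends on Table 6-3. Reach is also small: Amendment 7 records enrolment as complete in all three arms, with two patients still on drug on 23 July 2013. The case for correction is consistent safety management, at almost no cost.

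**What to change.** **Table 6-2, grade 3 row:** add the pneumonitis exception and referral to Table 6.3 that the grade 2 row already carries, or use one recovery threshold in both tables.

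**Table 6-3:**
- Replace cycles with weeks throughout.
- Grade 2: require the repeat CT and lung function by day 21, before the withdrawal decision.
- Grade 3: require the repeat before any restart, and state whether the 2 weeks run from the hold or from recovery.
- Grades 1 and 4: state an interval in weeks, chosen by the sponsor. The documents do not fix one; eight weeks for grade 1 would be an inference, and tumour imaging is 12 weeks apart after week 16.

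**Cost:** wording in two tables. The repeat tests are already required. Some would be done earlier, and an occasional patient would need an extra scan.
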